11.3.7. Electrocardiogram (ECG)

A 12-lead ECG will be performed at Screening (Visit 1) and will be reviewed by the Investigator for the purpose of excluding from participation patients who have either a history of or current evidence of clinically significant cardiac disease (e.g., significant arrhythmias or heart block, heart failure, or myocardial infarction within the past 2 years) or a QTcF at Screening >450m/sec (males) or QTcF >470m/sec (females).

The ECG interpretation by the Investigator will be recorded in the CRF as normal, abnormal but clinically insignificant, or abnormal and clinically significant. In addition, the standard ECG parameters including rhythm, heart rate, and intervals for PR (or PQ), QRS, and QTcF (Fridericia's) corrections for heart rate will be recorded.

If the Investigator has any concerns about the eligibility of a patient or wishes to confirm his/her assessment, the Investigator should consult with the medical monitor for this study.

11.3.8. Clinical Laboratory Assessments

The clinical laboratory evaluations to be performed in this trial are listed in [Table 2](#). Those marked as screening tests will be performed at screening only. All other tests will be performed at Screening (Visit 1) and after 12 weeks of treatment (Visit 6), or Early Termination. Clinical laboratory values may be repeated prior to randomization in order to confirm exclusionary levels for TSH, ALT and/or AST values. If these values remain persistently elevated upon repeat, the patient is not eligible for randomization.

With the exception of the urine pregnancy tests or the ad hoc urine drug test required at baseline for patients washing off excluded medications (e.g., opioids, benzodiazepines, amphetamines), all clinical laboratory evaluations will be analyzed via a central clinical laboratory, and information regarding appropriate sample volume, collection tubes, sample labeling and handling, and shipment will be provided in a study manual.

A urine drug screen for drugs of abuse (including marijuana) will be collected at Screening Visit 1 and sent to the central laboratory for analysis. If the patient has a positive drug screen at Visit 1 and/or Visit 2 for anything other than marijuana, and the results cannot be explained by use of current allowable prescription medications, the patient should be excluded from the study. If the urine drug screen is positive at Visit 1 and the results can be explained by the use of current prescription medications (e.g., opioids, benzodiazepines, amphetamines) that will be discontinued during screening, the investigator must repeat the drug screen and obtain a negative result using an in-clinic urine dipstick drug screen prior to randomization to confirm eligibility for the study.

Each clinically significant abnormal laboratory value or other clinically meaningful abnormality should be followed until the abnormality resolves or until a decision is made that it is not likely to resolve. If such abnormalities do not return to normal within a reasonable period, their etiology should be identified and Tonix or designee should be notified. Treatment-emergent clinically significant abnormalities in laboratory values will be recorded as AEs.

Table 2: Clinical Laboratory Assessments

Clinical chemistry	Hematology
Alanine aminotransferase (ALT) ^a	Hematocrit
Alkaline phosphatase	Hemoglobin
Aspartate aminotransferase (AST) ^a	MCH concentration (MCHC)
Bilirubin (total)	Mean corpuscular hemoglobin (MCH)
Blood urea nitrogen (BUN)	Mean corpuscular volume (MCV)
Calcium	Platelet count
Chloride	Red blood cell (RBC) count
Cholesterol (total)	WBC differential
Creatine kinase (CK)	Neutrophil count (absolute and %)
Creatinine	Lymphocyte count (absolute and %)
Glucose	Monocyte count (absolute and %)
Phosphorus	Eosinophil count (absolute and %)
Potassium	Basophil count (absolute and %)
Protein (albumin and total)	White blood cell (WBC) count
Sodium	
Thyroid-stimulating hormone (TSH)^c at screening	Serum Pregnancy Test at Screening^b
Free T4 only if TSH is outside of normal limits	Urine Pregnancy Test (qualitative dipstick)^b
Human immunodeficiency virus types 1 and 2 (HIV₁ and HIV₂)	Urine Drug Screen^d
Pharmacogenomic testing for invited participants at 5 study sites (optional) (Separate Visit post Week 12/ET)	

^a Level greater than 3 times the upper limit of normal is an exclusion (if persistent upon repeat).

^b Pregnancy testing for females of child-bearing potential only. A positive pregnancy test is exclusionary (Visit 1 or Visit 2) or mandates withdrawal from the study (all other visits).

^c TSH level greater than 1.5 times higher than the upper limit of normal is exclusionary at Visit 1.

^d Urine drug screening will be conducted on all patients at Screening and, if necessary, at Baseline in patients with a positive result at Screening who otherwise qualify for the study. For patients testing positive at the Screening visit for an excluded medication that will be discontinued during the screening interval, an in-clinic urine dipstick drug screen will be performed at the Baseline visit and must be negative for opioids, benzodiazepines, amphetamines and illicit drugs other than marijuana in order for the patient to be eligible for randomization.

11.3.9. Assessment of Changes in Sexual Function: Changes in Sexual Functioning Questionnaire Short-Form (CSFQ-14)

The Changes in Sexual Functioning Questionnaire Short-Form (CSFQ-14) (Keller et al. 2006) is a validated scale with internal reliability designed to allow a patient to self-evaluate his or her sexual behaviors or problems in a number of areas. The CSFQ-14 will be administered at Baseline (Visit 2) and Week 12/ET (Visit 6). It yields a total score, three subscales corresponding to phases of the sexual response cycle (i.e. desire, arousal, orgasm), and five subscales corresponding to important dimensions of sexual functioning. It is considered a useful scale for assessing sexual side effects of medications. For all items, higher scores reflect higher sexual functioning. For 12 of the 14 items, higher sexual functioning corresponds to greater

frequency or enjoyment/pleasure (e.g. 1=never to 5 = every day). For two items (item 10, assessing loss of interest after arousal for women and priapism for men, and item 14, assessing painful orgasm), higher sexual functioning corresponds to lower frequency (e.g. 1=every day to 5=never). Items 10 and 14 are included in the total score but not in any scale score.

11.3.10. Assessment of Sedation: Morning Treatment-Related Sedation Score (MTRSS)

The Morning Treatment-Related Sedation Score (MTRSS) is designed to assess the patient's morning sedation at clinic visits. The MTRSS will be assessed at Baseline (Visit 2) and at Weeks 4, 8, and 12/ET (Visits 4, 5, and 6). The patient will complete the following questions:

- A. On most mornings during the past week, I have awakened feeling:
0. Alert with no grogginess
 1. Mildly groggy
 2. Moderately groggy
 3. Very groggy
- B. If you reported any grogginess in the last week (responses 1-3), the grogginess lasted:
1. A few minutes
 2. A short time (less than one hour)
 3. A long time (more than one hour)

Note: if "Alert with no grogginess" is selected in Part A, Part B is not answered, and the score for part B is 0.

11.4. Pharmacogenomic Assessment

For pharmacogenomic analysis, a single blood sample collected in one PAXgene DNA tube will be obtained from an invited group of patients at 5 study sites after participation in the main study has ended. Patients had to have received active drug during the main study, at least one CAPS-5 assessment post-Baseline, and the patient has provided separate written, signed informed consent for pharmacogenomic analysis. The blood sample will be sent by the site to the pharmacogenomics testing laboratory where first DNA is extracted from the whole blood sample, and subsequently exome sequencing is performed on the DNA. The purpose of this testing is to allow exome sequencing and analysis for genetic variants related to treatment response and presence or absence of adverse events to TNX-102 SL.

12. DEFINITIONS, RECORDING, AND REPORTING OF ADVERSE EVENTS

12.1. Definition of Adverse Events

According to International Conference on Harmonization (ICH) guidance E2A, Clinical Safety Data Management: Definitions and Standards for Expedited Reporting, an adverse event (AE) is

any untoward medical occurrence in a patient or clinical investigation patient administered a pharmaceutical product and which is not necessarily required to have a causal relationship with this treatment. An AE can therefore be any unfavorable and unintended sign (including an abnormal laboratory finding, for example), symptom, or disease temporally associated with the use of a medicinal product, whether or not considered related to the medicinal product.

A treatment-emergent AE (TEAE) is an AE that either commenced following initiation of study treatment or was present prior to study treatment but increased in frequency or severity following initiation of study treatment.

12.2. Adverse Event Recording

12.2.1. Coding the Adverse Event

Standard medical terminology should be used in describing AEs. MedDRA[®] will be used as the standard coding dictionary for AEs and in describing the patient's medical history, and the World Health Organization (WHO) Drug Dictionary will be used to code concomitant medications. Informal descriptions should be avoided.

12.2.2. Severity of Adverse Event

AEs should be graded as mild, moderate, or severe using the following definitions.

- **Mild:** Awareness of signs or symptoms, but easily tolerated and of minor irritant type causing no loss of time from normal activities. Symptoms do not require therapy or a medical evaluation; signs and symptoms are transient.
- **Moderate:** Events introduce a low level of inconvenience or concern to the patient and may interfere with daily activities, but are usually improved by simple therapeutic measures; moderate experiences may cause some interference with functioning.
- **Severe:** Events interrupt the patient's normal daily activities and generally require systemic drug therapy or other treatment; they are usually incapacitating.

To make sure there is no confusion or misunderstanding of the difference between the terms "serious" and "severe," which are not synonymous, the following note of clarification is provided. The term "severe" is often used to describe the intensity (severity) of a specific event (as in mild, moderate, or severe myocardial infarction); the event itself, however, maybe of relatively minor medical significance (such as severe headache). This is not the same as "serious," which is based on patient/event outcome or action criteria usually associated with events that pose a threat to a patient's life or functioning. Seriousness (not severity) serves as a guide for defining regulatory reporting obligations.

12.2.3. Relationship of Adverse Events to Study Drug

The investigator will assess the potential relationship of the AE to study drug using the following descriptions.

- **Not Related:** This category applies to an AE that is clearly not related to the investigational agent/procedure, beyond a reasonable doubt. That is, another cause of the event is most plausible; and/or a clinically plausible temporal sequence is inconsistent

with the onset of the event and the administration of study drug and/or a causal relationship is considered biologically implausible.

- **Unlikely Related:** This category applies to an AE that could reasonably be considered caused by something else, and where there is no known or expected response pattern to the suspected study drug.
- **Possibly Related:** This category applies to an AE that follows a reasonable temporal sequence from administration of the study drug and that follows a known or expected response pattern to the suspected study drug, but that could readily have been produced by a number of other factors.

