case records and other documents when requested. Telephone and e-mail reports must be confirmed promptly either by facsimile or by email. For reporting SAEs, one of Tonix’s designated medical monitors should be called.

The Investigator or other study personnel must immediately inform one of the Tonix Medical Monitors by phone or email of any AE considered serious or otherwise significant, as described above. **In addition, a completed SAE report form must be submitted to [REDACTED] within 24 hours of initial awareness of the event.**

Contact information for the Medical Monitors is provided below:

Table 3: Medical Monitoring Contact Information

[REDACTED]	[REDACTED]	[REDACTED]
[REDACTED]	[REDACTED]	[REDACTED]
[REDACTED]	[REDACTED]	[REDACTED]
[REDACTED]	[REDACTED]	[REDACTED]
[REDACTED]	[REDACTED]	[REDACTED]
[REDACTED]	[REDACTED]	[REDACTED]
[REDACTED]	[REDACTED]	[REDACTED]

For questions pertaining to the reporting of SAEs or the completion of SAE documentation, site personnel should call [REDACTED]

The investigator, or the sponsor or designee in the case of a central Institutional Review Board (IRB), also must notify the EC/IRB of the occurrence of the SAE, in writing, as soon as is practicable and in accordance with local law. A copy of this notification must be provided to Tonix or its designee.

In the event of an SAE that meets the criteria for expedited reporting, an Investigational New Drug (IND) Safety Report will be prepared for submission to the FDA.

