#### 7.3.1 Adverse Event and Prior/Concomitant Medication handling conventions

To handle missing or partial AE and prior/concomitant medication dates, the following rules will be applied.

For partial start dates:

1. If the year is unknown, then do not impute the date but assign a missing value.
2. If the month is unknown, then:

- a. If the year matches the year of the first dose date, then impute the month and day of the first dose date.
  - b. Otherwise, assign “January.”
3. If the day is unknown, then:
- a. If the month and year match the month and year of the first dose date, then impute the day of the first dose date.
  - b. Otherwise, assign “01.”

For partial end dates:

1. If the year is unknown, then do not impute the date but assign a missing value.
2. If the month is unknown, then assign “December.”
3. If the day is unknown, then assign the last day of the month.

Adverse events are categorized as either pre-treatment adverse events or treatment-emergent adverse events based on the response to the CRF question “Did the AE start prior to the first dose?”

After implementing the rules above, to determine whether medications with missing start or stop dates are prior or concomitant medications, the following strategy will be used:

1. If the start date and stop date are both missing, then the most conservative approach is taken and the medication is considered to be a concomitant medication.
2. If the start date is missing but the stop date is not missing and is after the day of first study dose administration, then the most conservative approach is taken and the medication is considered to be concomitant.
3. If the start date is missing but the stop date is not missing and is on or before the day of first study dose and after the date of signed informed consent, then the medication is considered to be a prior medication.
4. If the start date is not missing but the stop date is missing, then the most conservative approach is taken and medication is considered to be concomitant.

The missing severity of an AE will be imputed to “severe”; the missing relationship to study drug of an AE will be imputed to “related”.

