### **10.1 Adverse Events**

All AEs, treatment-emergent adverse events (TEAEs), and SAEs will be coded using MedDRA, version 19.0.

TEAEs are defined as either new onset AEs with an onset at the time of or following the start of treatment through ten days after the last dose of study medication, or a recurrence of an AE (or medical history) present prior to randomization but increasing in severity, frequency or relationship at the time of or following the start of treatment

An AE summary table will be presented for the following:

- TEAEs by severity
- TEAEs leading to study drug discontinuation
- TEAEs by relationship
- SAEs

Summaries of incidence rates (frequencies and percentages) of individual AEs by MedDRA SOC and preferred term will be prepared. Such summaries will be displayed for all TEAEs, TEAEs by maximum severity, and TEAEs by strongest relationship to study drug.

Each participant will be counted only once within each summation level (SOC; preferred term). If a participant experiences more than one TEAE within each summation level only, the TEAE with the strongest relationship or the maximum severity, as appropriate, will be included in the summaries of relationship and severity.

Adverse events of special interest pertaining to abuse potential (as defined in the January 2017 Assessment of Abuse Potential for Drugs – Guidance for Industry) will be analyzed separately by treatment group, SOC and preferred term, and displayed in tabular format.

In the AE data listings, all AEs will be displayed. AEs that are treatment-emergent will be flagged.

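### The three causality levels in Protocol 12.2.3 cap some plausible drug reactions at 'Unlikely Related' and leave others with no level, and SAP 7.3.1 imputes to a level the protocol does not define

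*Protocol*

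**What the plan says.** Protocol 12.2.3 makes the scale binding: "The investigator will assess the potential relationship of the AE to study drug using the following descriptions". Three descriptions follow, and the text then moves on to SAEs in 12.3.

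- *Not Related*: the event is "clearly not related to the investigational agent/procedure, beyond a reasonable doubt". The protocol explains this as another cause being most plausible, timing that does not fit, or biological implausibility.
- *Unlikely Related*: the event "could reasonably be considered caused by something else, and where there is no known or expected response pattern to the suspected study drug".
- *Possibly Related*: the event "follows a reasonable temporal sequence from administration of the study drug" and also "follows a known or expected response pattern to the suspected study drug, but that could readily have been produced by a number of other factors".

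Protocol 11.3.1 has causality recorded on the CRF for AEs, and Protocol 13.5 plans AE summaries by relationship. SAP 10.1 plans summaries of "TEAEs by maximum severity, and TEAEs by strongest relationship to study drug". For blanks, SAP 7.3.1 states that "the missing relationship to study drug of an AE will be imputed to" 'related'. Neither document defines a level called 'related', 'probably' or 'definitely'.

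**The concern.** Two different questions are mixed in one scale. Causality asks whether the drug produced this event. Expectedness asks whether the drug is already known to produce such events. In Protocol 12.2.3 the second is a necessary condition for the highest answer to the first. A second necessary condition is that something else could readily explain the event, so the clearest drug reactions fail the top level for lack of a rival cause.

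New reactions are a real possibility here. Protocol 5 says the approved brands are indicated for 2-3 weeks, while this trial gives a sublingual form for 12 weeks. The clear-cut known reaction is not hypothetical either: Protocol 11.3.5 itself names tongue numbness, tingling and bitter taste as transient sensory oral events. Where no description fits, each of about 45 sites must improvise, and the by-relationship tables would pool ratings made under different private rules.

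**Working it through.** No arithmetic applies; the check is to match every type of event to the definitions. Take an event with plausible timing and plausible biology. The definitions then turn on two attributes: whether there is a known or expected pattern, and whether there is another reasonable or ready cause.

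| | Known pattern | Other cause | Highest level whose description is met |
|---|---|---|---|
| 1 | yes | yes | *Possibly Related* |
| 2 | yes | no | none |
| 3 | no | yes | *Unlikely Related* |
| 4 | no | no | none |

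**Row 1** meets all three conditions of *Possibly Related*.

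**Row 2**, such as tongue numbness straight after a sublingual dose with nothing else to explain it, fails *Possibly Related* because no other factor could readily have produced it. It fails *Unlikely Related* on both of that level's conditions. It is not clearly unrelated.

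**Row 3** fails *Possibly Related* for want of a known pattern and meets *Unlikely Related*. *Not Related* could apply only if the other cause were clear beyond reasonable doubt, which would be lower still.

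**Row 4** fails *Possibly Related* on both extra conditions. It also fails *Unlikely Related*, which needs a reasonable other cause.

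So 1 of 4 combinations reaches the top level, 1 of 4 is capped one level down, and 2 of 4 have no description.

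**Imputation.** The highest level an investigator can assign under Protocol 12.2.3 is *Possibly Related*. The value imputed for a blank is 'related'. On the natural ordering, with 'related' above 'possibly related', a blank outranks every rating the protocol allows. SAP 10.1 keeps the strongest relationship per participant within each SOC and preferred term, so one blank would displace a real *Possibly Related* rating in that table.

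**Where the rating is used.** It enters the by-relationship summaries (Protocol 13.5, SAP 10.1). It does not decide which SAEs go to the sponsor: Protocol 12.3 requires every SAE to be reported, and deaths whatever the view on cause. The SAP 10.1 tables of all TEAEs, and those in 10.1.1 and 10.1.2 for discontinuations and SAEs by arm, are not selected on causality. There is one narrow qualification. The TEAE definition in SAP 10.1 counts a pre-existing event as treatment-emergent if its relationship increases, among other criteria. Protocol 12.1 has no such clause, and SAP 7.3.1 takes TEAE status from a CRF question on whether the event started before the first dose, so little rests on it.

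**The case against.** **A fourth level may exist.** The SAP's value 'related' suggests that the CRF offers such an option. The CRF is not among the documents, and no redaction is marked at this point in 12.2.3, so this cannot be settled. If the option exists, row 2 and arguably row 4 have somewhere to go, but under a level the protocol leaves undefined, and row 3 is still capped. The mismatch between protocol and SAP needs reconciling either way.

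**'Expected' is broader than 'already known'.** It could cover effects anticipated from pharmacology, and the label in Protocol Appendix 3 lists reactions across many organ systems. This stands in part: fewer events fall in rows 3 and 4. It does not help row 2.

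**Investigators will use judgment.** Probably so, and many would choose *Possibly Related* for rows 2 and 4. That weakens any claim about the direction of error, but it concedes that the written rule does not decide these cases.

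**Detection does not rest on this scale.** This stands. A reader might infer that serious new reactions could go unreported. The documents do not support that: SAE reporting is independent of causality, and the sentence beginning "In the event of an SAE that meets the criteria for expedited reporting" in Protocol 12.3 does not mention the investigator's rating. The trial is randomized and placebo-controlled, and new reactions can show in the all-TEAE tables by arm.

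**Conclusion.** The definitions are wrong as written, and the consequence is modest. On the literal wording, for events with plausible timing and biology, two of four combinations have no level and one is capped at *Unlikely Related*. The SAP's imputed value lies outside the protocol's scale. The damage is confined to the by-relationship AE summaries and any later decision that draws on investigator causality.

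A reader might go further and infer that no previously unknown reaction can ever be rated above *Unlikely Related*, or that related counts are biased downward by a known amount. Neither follows. Row 4 has no defined level, so its rating is left to choice and could be *Possibly Related*. The four rows are logical cells, not frequencies. The documents do not say which levels would be pooled as related, and imputing blanks to 'related' pushes the count upward.

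The conclusion assumes that sites apply 12.2.3 as worded and that no other document, such as CRF instructions, supplies further definitions.

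**What to change.** In Protocol 12.2.3:

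1. Define the top level, whether a new *Related* or a redefined existing one, as plausible timing and a reasonable possibility that study drug caused the event, whether or not the reaction is already known and whether or not another cause is also possible.
2. Remove the known pattern and the ready alternative cause as necessary conditions for *Possibly Related*. If both *Related* and *Possibly Related* are kept, state what separates them.
3. Base *Unlikely Related* on another cause being more likely, and delete its condition on response pattern.
4. Keep expectedness as a separate sponsor assessment.

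In the SAP, make the imputation value in 7.3.1 and the relationship tables in 10.1 use exactly the levels defined in the protocol.

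The cost is one protocol paragraph, the CRF completion guideline and matching SAP text, with no new data collection. Related counts may rise slightly. The Protocol synopsis puts the last patient's completion at January 2019 and the added post-study assessment at November 2019, so events may already have been rated under the present wording. In that case the tables should state which definitions applied, rather than mix two scales without comment.
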